Study Purpose and Rationale	
IMCgp100-102 is a Phase 1/2 study of the weekly (QW) intra-patient escalation dose regimen with IMCgp100 as a single agent in patients with metastatic uveal melanoma (mUM). The Phase 1 testing of this regimen will aim to achieve a higher exposure and maximal plasma concentration of IMCgp100 after doses at Cycle 1 Day 15 (C1D15) and thereafter than the exposures achievable at the recommended Phase 2 dose (RP2D) of the fixed QW dose of 50 mcg (RP2D-QW) without additional toxicity. Phase 1 testing will follow the standard 3+3 design with dose-limiting toxicity (DLT) as the endpoint and identification of the maximum tolerated dose (MTD) and/or the RP2D for the intra-patient escalation regimen (RP2D-IE).
 
In the Phase 1 first-in-human (FIH) study of IMCgp100 in advanced melanoma, a dose escalation was conducted with IMCgp100 administered on a QW basis. Results of this study have been presented (Middleton, 2015). In this study, the MTD when IMCgp100 is administered on a QW basis was determined to be 600 ng/kg. With a data cut off of 18 August 2015, it was observed that DLT of grade 3 (n=3) and 4 (n=1) hypotension in the QW dosing cohort was observed with the first or second dose in this trial. Based on observed safety and the pharmacokinetic (PK) profile a flat dosing regimen was implemented across the program and the RP2D of the weekly schedule (RP2D-QW) was identified as 50 mcg QW. This dose and regimen have been adjusted based on emerging safety in the trial and dosing adjustments were implemented in the FIH QW dosing expansion cohort (IMCgp100-01, NCT01211262).

[figure not shown]
	
In this same FIH study, several patients with mUM were treated in the QW dosing regimen at the MTD dose level (600 ng/kg) and at the dose level above MTD, 900 ng/kg (n=5, data cut off 18 August 2015). Based on review of the observed objective responses in the Phase 1 trial in uveal melanoma (UM) as well as objective responses noted in cutaneous melanoma, it was noted that patients with larger diameters of disease burden (both cutaneous and UM) experienced objective tumor responses at the higher overall exposures to IMCgp100.
 
The current study of the intra-patient dose escalation regimen is based on 2 observations in the clinic: (1) objective partial and minor tumor responses in patients with higher tumor burdens were generally observed at the higher absolute doses in the Phase 1 trial, and (2) the occurrences of more severe toxicity leading to dose limitation were limited to the first 2 weeks of dosing on C1D1 and C1D8. Based on these 2 observations, it is hypothesized that an increased exposure to drug in the weeks following the occurrence of the more severe toxicity (at the first 2 doses) may lead to an enhanced tumor response in a setting of an unfavorable tumor microenvironment such as UM.

Primary Objectives	
Phase 1 Dose Escalation: The primary objective is to identify the MTD and/or the RP2D of IMCgp100 in the intra-patient dose escalation regimen (RP2D-IE).
 
Phase 2 Dose Expansion: The primary objective is to estimate the objective response rate by independent central review (ICR) based on Response Evaluation Criteria in Solid Tumors version 1.1 (RECISTv1.1) in patients with advanced UM who are treated with the RP2D-IE of IMCgp100.

Secondary Objectives	
• To characterize the safety and tolerability of IMCgp100 in the intra-patient dose escalation regimen• To characterize the PK profile of single-agent IMCgp100 in the intra-patient dose escalation regimen• To assess the anti-tumor efficacy of IMCgp100 with the parameters of objective response rate (Phase 1), overall survival, progression-free survival (PFS), disease control rate (DCR), time to response, and the duration of response (DOR).• To evaluate the incidence of anti-IMCgp100 antibody formation following multiple infusions of IMCgp100 in the intra-patient dose escalation regimen• To determine the rate and duration of minor responses (defined as tumor response with a reduction in the sum of longest diameters of

	10%–29%) and immune responses (as assessed by area under the tumor response curves [AUC])
Study Design	
This is a Phase I12 study of IMCgp100 administered on a QW basis with an intra-patient escalation dosing regimen. The intra-patient escalation occurs at the third QW dose on C1D15. According to this regimen, all patients in the trial will receive 2 QW doses of IMCgp100 at a dose level below the identified RP2D-QW, and then a dose escalation will commence at the third QW dose at C1D15 with the goal to achieve a long-term dosing regimen at a dose higher than that identified for the RP2D-QW. In this dosing regimen, each patient will undergo a fixed intra-patient dose escalation (fixed dosing of 20 mcg at C1D1 and 30 mcg at C1D8), followed by the dose escalation beginning at C1D15. Patients will continue to receive the same escalated dose from C1D15 and thereafter. The dose escalation will identify the RP2D-IE.
 
The Phase 1 portion of the study will be a standard 3+3 dose escalation design. After the dose escalation portion is complete and the MTD or the RP2D-IE is identified, the Phase 2 expansion cohorts in mUM will be enrolled. These two cohorts will enroll patients with mUM and will enroll approximately 150 patients combined.
 
 • Cohort A will enroll patients with mUM in the second-line setting after disease progression following systemic treatment with a checkpoint inhibitor with any prior liver directed therapy (LDT) • Cohort B will enroll patients with mUM in the second or third-line setting with up to one prior LDT regimen • Additional details regarding expansion cohorts are outlined in Key Inclusion Criteria below, Section 3.2 and Section 5.2.
Population Under Study	
The trial will enroll patients with a diagnosis of advanced mUM, defined as histologically confirmed diagnosis of UM and metastatic stage IV disease at study entry. In the Phase 1 dose escalation portion of the trial, patients are eligible with any prior therapy including systemic treatments or LDT with an Eastern Cooperative Oncology Group (ECOG) performance score of 0 or 1 and meeting all additional eligibility criteria.
 
Once the dose is identified in the Phase 1 dose escalation, 2 Phase 2 expansion cohorts will be enrolled in 2 patient populations:
 
 1. Cohort A: Patients will have experienced disease progression with 1 systemic treatment regimen containing a checkpoint inhibitor, including either a CTLA4 inhibitor (ipilimumab or

	
tremelimumab) and/or a PD-1/PD-L1 inhibitor. Any prior LDT is acceptable in this cohort.
 
2. Cohort B will enroll patients with mUM in the second or third-line setting with up to one prior LDT regimen.
 
Additional details regarding expansion cohorts are outlined in Key Inclusion Criteria below, Section 3.2 and Section 5.2
 
These Phase 2 expansion cohorts are designed to further characterize the safety, tolerability, and preliminary PK and anti-tumor activity of IMCgp100.

Key Inclusion Criteria	
1. Male or female patients age \geq 18 years of age at the time of informed consent2. Ability to provide and understand written informed consent prior to any study procedures3. Histologically or cytologically confirmed diagnosis of mUM4. Surgically sterile patients or patients of child-bearing potential who agree to use highly effective methods of contraception during study dosing and for 6 months after last dose of study drug5. Life expectancy of > 3 months as estimated by the investigator6. Human leukocyte antigen-A*0201 positive by central assay7. ECOG Performance Status of 0 or 1 at Screening8. Patients must have disease (measurable or non-measurable acceptable) according to RECIST v.1.1 criteria in the Phase 1 dose escalation cohorts. Patients must have measurable disease in the Phase 2 dose expansion cohorts9. Phase 1 dose escalation cohorts only: any prior therapy is acceptable10. Phase 2 dose expansion cohorts:
• Cohort A: Patients will have experienced disease progression with 1 systemic treatment regimen containing a checkpoint inhibitor, including either a CTLA4 inhibitor (ipilimumab or tremelimumab) and/or a PD-1/PD-L1 inhibitor. Any prior LDT is acceptable in this cohort• Cohort B: Patients will have experienced disease progression with 1 or 2 prior lines of therapy in the metastatic or advanced setting including chemotherapy, immunotherapy or targeted therapy. Only a single line of local, LDT including chemotherapy, radiotherapy, radiofrequency ablation or embolization is allowed. A line of LDT is defined as one

	
modality of treatment that is administered until completion of treatment or disease progression. For patients who have received prior LDT, this will count as a line of therapy. Prior surgical resection of oligometastatic liver disease is allowed and is not counted as a line of LDT. A patient may have discontinued systemic therapy prior to disease progression if the patient experienced a significant adverse reaction that required treatment discontinuation, as per Investigator's judgment and applicable labelling. Prior checkpoint inhibitor therapy is acceptable but not required in this cohort.
 
A. This means patients with the following treatments are eligible under Cohort B:
 
  1 systemic therapy and 1 LDT  1 – 2 systemic therapies and 0 LDT  0 systemic therapy and 1 LDT 
b. Adjuvant therapies and local therapies for treatment of disease outside of the liver do not count towards the lines of prior therapy.
 
11. All other relevant medical conditions must be well-managed and stable, in the opinion of the investigator, for at least 28 days prior to first administration of study drug

Key Exclusion Criteria	
 1. Presence of symptomatic or untreated central nervous system (CNS) metastases, or CNS metastases that require doses of corticosteroids within the prior 3 weeks to study Day 1. Asymptomatic and adequately treated CNS metastases are not exclusionary 2. History of severe hypersensitivity reactions to other biologic drugs or monoclonal antibodies 3. Patient with any out-of-range laboratory values defined as: 
 • Serum creatinine > 1.5 x upper limit of normal (ULN) and/or creatinine clearance (calculated using Cockcroft-Gault formula, or measured) < 50 mL/min • Total bilirubin > 1.5 x ULN, except for patients with Gilbert's Syndrome who are excluded if total bilirubin > 3.0 x ULN or direct bilirubin > 1.5 x ULN • Alanine aminotransferase (ALT) > 3 x ULN

	
 Aspartate aminotransferase (AST) > 3 x ULN Absolute neutrophil count < 1.0 x 10⁹/L Absolute lymphocyte counts: (1) Phase 1 and Phase 2 Expansion Cohort A: Absolute lymphocyte count < 0.5 x 10⁹/L; (2) Phase 2 Expansion Cohort B: Absolute lymphocyte count < 1.0 x 10⁹/L Platelet count < 75 x 10⁹/L Hemoglobin < 8 g/dL Potassium, magnesium, corrected calcium or phosphate abnormality of National Cancer Institute Common Terminology Criteria for Adverse Events (NCI CTCAE) > grade 1 
4. Phase 1 dose escalation only: Presence of high tumor burden, defined as liver replacement of > 60% hepatic organ volume with tumor
 
5. Clinically significant cardiac disease or impaired cardiac function, including any of the following:
 
 Clinically significant and/or uncontrolled heart disease such as congestive heart failure (New York Heart Association grade ≥ 2), uncontrolled hypertension or clinically significant arrhythmia currently requiring medical treatment QTcF > 470 msec on screening electrocardiogram (ECG) or congenital long QT syndrome Acute myocardial infarction or unstable angina pectoris < 6 months prior to Screening 
6. Patients may not have been included in any prior IMCgp100 trial, regardless of assigned treatment cohort

Efficacy Assessments	
Radiologic assessments should be performed as scheduled every 8 or 12 weeks using a reference to C1D1 and should NOT follow delays incurred in the treatment period.
 
Tumor response will be determined according to 2 sets of criteria:
 
 RECIST v.1.1 Modified immune-related response criteria (irRECIST) for patients who continue treatment beyond RECISTv1.1 progression 
Phase 1: The local investigator's assessment will be used for the analysis of response according to RECIST v.1.1 for efficacy endpoints of the study

	
and modified irRECIST, and for treatment decision making (study discontinuation due to progressive disease [PD] as per RECISTv.1.1/modified irRECIST).
 
Phase 2: For the expansion cohorts only, an independent central review (ICR) will be used for the analysis of objective response rate and all other tumor-related endpoints based on RECIST v.1.1 and irRECIST. Investigator assessment data will be used for treatment decision making during the study.
 
PFS will be assessed using RECIST v.1.1. Patients experiencing PD per RECIST v.1.1 criteria may consent to continue to be treated according to irRECIST guidelines until confirmed, unequivocal progression is documented via modified irRECIST. Progression based on modified irRECIST will be assessed as an exploratory endpoint.
 
Imaging per CT or MRI will be performed at baseline and scheduled follow-up timepoints- additional details are outlined in Section 7.3.1.

Safety Assessments	Safety will be monitored by assessing physical examination, vital signs, body height and weight, performance status, hematology, chemistry, coagulation, urinalysis, thyroid function, pregnancy, ECG, cytokine testing, as well as collecting of the adverse events at every visit.
Biomarker Assessments	

Keywords	IMCgp100, uveal melanoma, T cell redirection, gp100

List of Abbreviations

AE	Adverse event
AESI	Adverse event of special interest
Akt	Protein kinase B
ALT	Alanine aminotransferase
anti-CD3	Anti-cluster of differentiation 3
AST	Aspartate aminotransferase
AUC	Area under the curve
C#D#	Cycle 1 Day 1; Cycle 8 Day 1; Cycle 15 Day 1; Cycle 2 Day 15
C1D8	Cycle 1 Day 8
CD3	Cluster of differentiation 3
C _{max}	Maximum observed concentration
CNS	Central nervous system
CR	Complete response
CRO	Contract research organization
CRP	C-reactive protein
CRS	Cytokine release syndrome
CT	Computed tomography
CTCAE	Common Terminology Criteria for Adverse Event
ctDNA	Circulating tumor deoxyribonucleic acid
CTL	Cytotoxic T lymphocyte
CTLA-4	Cytotoxic T lymphocyte associated protein-4
DCR	Disease control rate
DETC	Dose escalation teleconference
DLT	Dose-limiting toxicity
ECG	Electrocardiogram
ECOG	Eastern Cooperative Oncology Group
eCRF	Electronic case report form
EDC	Electronic data capture
EOT	End of treatment
FAS	Full analysis set

FIH	First-in-human
GCP	Good clinical practice
GNAQ	Heterotrimeric G protein alpha subunit q
GNA11	Heterotrimeric G protein alpha subunit 11
HBV	Hepatitis B virus
HCV	Hepatitis C virus
HIV	Human immunodeficiency virus
HLA	Human leukocyte antigen
HLA-A2	Human leukocyte antigen-A2
HLA-A*0201	Human leukocyte antigen-A*0201
HLA-DR	Human leukocyte antigen-DR
HRQoL	Health-related quality of life
IDMC	Independent data monitoring committee
ICH	International Conference on Harmonization
ICR	Independent central review
IEC	Independent Ethics Committee
IFN- γ	interferon gamma
IHC	Immunohistochemistry
IL-#	Interleukin-# (e.g., IL-6, IL-10)
IMCgp100	77 kDa bi-specific protein
IRB	Institutional Review Board
irPD	Immune-related progressive disease
irRC	Immune-related response criteria
irRECIST	Immune-related response criteria in solid tumors
IV	Intravenous
LDH	Lactate dehydrogenase
LDT	Liver-directed therapy
LFT	Liver function test
MEK	Mitogen-activated protein kinase/ Extracellular signal-regulated kinase
MinR	Minor response
MRI	Magnetic resonance imaging
MTD	Maximum tolerated dose
mUM	Metastatic uveal melanoma
NCI CTCAE	National Cancer Institute Common Terminology Criteria for Adverse Events

ORR	Objective response rate
OS	Overall survival
PBMC	Peripheral blood mononuclear cells
PD	Progressive disease
PD-1	Programmed death-1
PD-L1	Programmed death-ligand 1
PFS	Progression-free survival
PK	Pharmacokinetics
PI3-kinase	Phosphatidylinositol 3-kinase
PPS	Per protocol set
PR	Partial response
QD	Every day
QW	Every week
REB	Research ethics board
RECIST	Response Evaluation Criteria in Solid Tumors
RNA	Ribonucleic acid
RP2D	Recommended Phase 2 dose
RP2D-IE	Recommended Phase 2 dose — intra-patient escalation
RP2D-QD	Recommended Phase 2 dose — daily
RP2D-QW	Recommended Phase 2 dose — weekly
SAE	Serious adverse event
SAP	Statistical Analysis Plan
SD	Stable disease
SLD	Sum of longest diameters
SUSAR	Suspected, unexpected, serious adverse reaction
$t_{1/2}$	half-life
TIL	Tumor infiltrating lymphocyte
TMTB	total measured tumor burden
ULN	Upper limit of normal
UM	Uveal melanoma

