5.2 Inclusion Criteria

Patients eligible for inclusion in this study must meet **all** of the following criteria:

1. Male or female patients age \geq 18 years of age at the time of informed consent
2. Ability to provide and understand written informed consent prior to any study procedures
3. Histologically or cytologically confirmed diagnosis of metastatic UM
4. Surgically sterile patients or patients of child-bearing potential who agree to use highly effective methods of contraception during study dosing and for 6 months after last dose of study drug
5. Life expectancy of $>$ 3 months as estimated by the investigator
6. HLA-A*0201 positive by central assay
7. ECOG Performance Status of 0 or 1 at Screening
8. Patients must have disease (measurable or non-measurable acceptable) according to RECIST v.1.1 criteria in Phase 1 dose escalation cohorts. Patients must have measurable disease in the Phase 2 dose expansion cohorts
9. Phase 1 dose escalation cohorts only: any prior therapy is acceptable

Prior therapy in Phase 2 expansion cohorts:

- Cohort A: Patients will have experienced disease progression with 1 systemic treatment regimen containing a checkpoint inhibitor, including either a CTLA4 inhibitor (ipilimumab or tremelimumab) and/or a PD-1/PD-L1 inhibitor. Any prior LDT is acceptable in this cohort
- Cohort B: Patients will have experienced disease progression with 1 or 2 prior lines of therapy in the metastatic or advanced setting including chemotherapy, immunotherapy or targeted therapy. Only a single line of local, LDT including chemotherapy, radiotherapy, radiofrequency ablation or embolization is allowed. A line of LDT is defined as one modality of treatment that is administered until completion of treatment or disease progression. For patients who have received prior LDT, this will count as a line of therapy. Prior surgical resection of oligometastatic liver disease is allowed and is not counted as a line of LDT. A patient may have

discontinued systemic therapy prior to disease progression if the patient experienced an adverse reaction that required treatment discontinuation, as per Investigator's judgment and applicable labelling. Prior checkpoint inhibitor therapy is acceptable but not required in this cohort.

- a. This means patients with the following treatments are eligible under Cohort B:
 - 1 systemic therapy and 1 LDT
 - 1 – 2 systemic therapies and 0 LDT
 - 0 systemic therapy and 1 LDT

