9.6 Secondary Analyses

9.6.1 Efficacy

Analysis of efficacy endpoints will be performed using the FAS unless otherwise noted.

For the Phase 1 escalation cohorts, tumor-based endpoints will be assessed using local investigator assessment and ICR where available for both RECISTv.1.1 and modified irRECIST. For the Phase 2 expansion cohorts, tumor-based endpoints will be assessed using ICR data for both RECIST v1.1 and modified irRECIST. ORR and other RECIST-based endpoints as assessed by the local radiologist will be summarized as a sensitivity analysis.

ORR is defined as the proportion of patients with measurable disease with at least 1 visit response of CR or PR that is confirmed at least 4 weeks later, as defined in RECIST v.1.1.

The denominator in the calculation of the ORR will be the number of patients in the FAS with measurable disease at baseline. Data obtained up until progression, or last evaluable assessment in the absence of progression, will be included in the assessment of ORR. However, any CR or PR, which occurred after further anti-cancer therapy was received, will not be included in the numerator of the ORR calculation. Disease control rate is defined as the proportion of patients with a best overall response of CR or PR or SD recorded at least 24 weeks (\pm 1 week) after commencement of study drug and prior to any PD event.

For all efficacy parameters, data will be listed, summarized, or analyzed by treatment group (dose cohort) for the Phase 1 dose escalation and overall for the Phase 2 expansion cohorts.

In order to explore whether the Phase 2 efficacy results are consistent across prior therapy groups, key endpoints (including ORR and DoR) may be further summarized by prior therapy groups (for example: 1 systemic therapy and 1 LDT; 1-2 systemic therapies only; 1 LDT only, 1 checkpoint inhibitor and any LDT).

Further subset analyses of efficacy by LDH (above or below institutional ULN) and hepatic metastases (present or absent) may be performed if an adequate number of patients with and without the prognostic factor are available for analysis (Valpione, 2015).

ORR and DCR will be summarized with accompanying 95% confidence intervals.

PFS, along with DOR and time to response for patients who experience a CR or PR at any time on study will be listed by patient.

[figure not shown]

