13.1.6 Determination of Non-target Lesion Response

Table 13-2 Response Criteria for Non-target Lesions

Response Criteria	Evaluation of Non-target Lesions
Complete Response	Disappearance of all non-target lesions. In addition, all lymph nodes assigned non-target lesions must be non-pathological in size (< 10 mm short axis)
Progressive Disease	Unequivocal progression of existing non-target lesions ¹
Non-complete response/ Non-progressive disease	Neither complete response nor progressive disease

1. Although a clear progression of non-target lesions only is exceptional, in such circumstances, the opinion of the treating physician does prevail and the progression status should be confirmed later on by the central review.

Non-target Lesion Response

- The response for non-target lesions is CR only if all non-target non-nodal lesions which were evaluated at Baseline are now all absent and with all non-target nodal lesions returned to normal size (i.e., < 10 mm). If any of the non-target lesions are still present, or there are any abnormal nodal lesions (i.e., ≥ 10 mm) the response can only be ‘Non-CR/Non-PD’
- Unequivocal progression: To achieve “unequivocal progression” on the basis of non-target disease there must be an overall level of substantial worsening in non-target disease such that, even in presence of CR, PR, or stable disease (SD) in target disease, the overall tumor burden has increased sufficiently to merit discontinuation of therapy. In order for a PD to be assigned on the basis of non-target lesions, the increase in the extent of the disease must be substantial even in cases where there is no measurable disease at Baseline

New Lesions

The appearance of a new lesion is always associated with PD and has to be recorded as a new lesion in the eCRF.

- If a new lesion is equivocal, for example because of its small size, continued therapy and follow-up evaluation will clarify if it represents truly new disease. If repeat scans confirm there is definitely a new lesion, then progression should be declared using the date of the first observation of the lesion
- If new disease is observed in a region which was not scanned at Baseline or where the particular baseline scan is not available for some reason, then this should be considered PD
- A lymph node is considered as a “new lesion” and, therefore, indicative of PD if the short axis increases in size to ≥ 10 mm for the first time in the study plus 5 mm absolute increase

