13.1.7 Evaluation of Overall Lesion Response

The evaluation of overall lesion response at each assessment is a composite of the target lesion response, non-target lesion response and presence of new lesions as shown below in Table 13-3.

Table 13-3 Overall Lesion Response at Each Assessment

Target Lesions	Non-target Lesions	New Lesions	Overall Lesion Response
CR	CR	No	CR ¹
CR	Non-CR/Non-PD	No	PR
PR	Non-PD	No	PR ¹
SD	Non-PD	No	SD ^{1,2}
PD	Any	Yes or No	PD
Any	PD	Yes or No	PD
Any	Any	Yes	PD

CR = complete response; PD = progressive disease; PR = partial response; SD = stable disease.

1. This overall lesion response also applies when there are no non-target lesions identified at Baseline.
2. Once confirmed PR was achieved, all these assessments are considered PR.

References:

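### The Phase 1 disease control rate cannot count stable patients who have only non-measurable disease, although they are eligible and stay in its denominator

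*Protocol*

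**What the plan says.** **Eligibility.** The Synopsis (Key Inclusion Criteria, item 8) states: "Patients must have disease (measurable or non-measurable acceptable) according to RECIST v.1.1 criteria in the Phase 1 dose escalation cohorts". Section 5.2 (criterion 8) gives the same rule: "Patients must have disease (measurable or non-measurable acceptable) according to RECIST v.1.1 criteria in Phase 1 dose escalation cohorts". The expansion cohorts, by contrast, require measurable disease.

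**Analysis set.** Section 9.6.1: "Analysis of efficacy endpoints will be performed using the FAS unless otherwise noted". Section 9.2.1 defines the Full Analysis Set (FAS) as everyone assigned to treatment who received any IMCgp100, with no condition on measurability.

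**Endpoints.** For response, Section 9.6.1 makes an exception to the plain FAS: "The denominator in the calculation of the ORR will be the number of patients in the FAS with measurable disease at baseline". For disease control it makes none: "Disease control rate is defined as the proportion of patients with a best overall response of CR or PR or SD recorded" at 24 weeks or later (± 1 week) and before any progression. Section 4.5 lists DCR as a secondary endpoint under RECIST v1.1. Section 9.6.1 presents Phase 1 efficacy by dose cohort.

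**Response categories.** In Appendix 1, Table 13-1 defines PR and SD from the sum of target-lesion diameters. Table 13-2 offers three non-target categories: CR, PD, and Non-CR/Non-PD, the last described as "Neither complete response nor progressive disease". Table 13-3 combines target, non-target and new-lesion findings into the overall response. Its footnote 1 reads: "This overall lesion response also applies when there are no non-target lesions identified at Baseline".

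**The concern.** The eligibility rule admits a type of patient for whom the response tables provide no stable category, and the DCR definition then requires that category. A patient with only non-measurable disease has no target lesions and so no sum of diameters, and cannot be classed as PR or SD. If the disease stays stable past 24 weeks, the patient has what DCR is meant to capture, yet does not meet its definition.

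The error runs in one direction, towards too low a DCR. Its size in each dose cohort depends on how many patients happened to lack measurable disease at baseline, which has nothing to do with dose. With cohorts of 3 to 6 patients, a single case can visibly change a cohort's figure and blur the descriptive comparison across doses.

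**Working it through.** The protocol gives no DCR figure, so there is none to reproduce. The check is to follow one patient through the text and then work out the effect of each such patient.

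**Tracing the patient**

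Take a Phase 1 patient with only non-measurable disease, treated, stable, and free of progression at 24 weeks.

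1. Eligible: yes (Synopsis item 8; Section 5.2, criterion 8).
2. In the FAS: yes, because the patient was treated (Section 9.2.1).
3. In the DCR denominator: yes. The FAS is the default and the measurable-disease restriction is written for ORR only (Section 9.6.1).
4. Target-lesion response: none, because there are no target lesions (Table 13-1).
5. Non-target response: Non-CR/Non-PD (Table 13-2).
6. Overall response in Table 13-3:
   - The rows leading to CR, PR and SD each specify a target-lesion response of CR, PR or SD.
   - Only the rows that accept any target status can apply, and both lead to PD. This patient meets neither.
   - Footnote 1 covers the reverse case, target lesions present and non-target lesions absent.
   - The overall response is therefore unassigned.
7. In the DCR numerator: no. Neither an unassigned response nor Non-CR/Non-PD is CR, PR or SD.

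Section 13.1.6 does foresee patients with no measurable disease at baseline, but only when setting the threshold for declaring progression. Appendix 1 thus says how such a patient progresses and never how the patient is stable.

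**Effect of each affected patient**

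One stable patient wrongly left out of the numerator lowers the DCR by 1/n. Section 6.3.4 gives cohorts of 3 to 6.

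- n = 3: 1/3 = 33.3 points (for example 1/3 falls to 0/3).
- n = 6: 1/6 = 16.7 points (for example 3/6 falls to 2/6).

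**Illustration in a cohort of 6**

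Suppose three patients are progression-free at 24 weeks and one of these has only non-measurable disease. Intervals are Clopper-Pearson 95%.

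| Rule | DCR | 95% CI |
|---|---|---|
| As written | 2/6 = 33% | 4% to 78% |
| Non-CR/Non-PD counted | 3/6 = 50% | 12% to 88% |
| Denominator limited to measurable disease | 2/5 = 40% | 5% to 85% |

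**Illustration for pooled Phase 1**

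Let m of n patients have only non-measurable disease, and let p be the true disease control rate, the same in both groups. Take complete disappearance of non-target disease as negligible. Then the expected DCR as written is p(n − m)/n, and the shortfall is p × m/n. The values of n, m and p below are assumptions; the protocol gives none of them.

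- Low end: n = 24, m = 1, p = 0.30 gives 0.30 × 1/24 = 1.3 points.
- High end: n = 18, m = 4, p = 0.50 gives 0.50 × 4/18 = 11.1 points.
- With m = 0 the shortfall is zero.

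**The case against.** The strongest reply is that this is a gap and not a wrong rule. No sentence in the protocol calls these patients failures. Non-CR/Non-PD is a lesion-level category, the overall response is simply undefined for them, and Section 9.6.1 leaves further detail on the Phase 1 summaries to the SAP. It is true that the failure is a consequence of the text and not a statement in it. But the protocol fixes the numerator as CR, PR or SD and fixes the analysis set by default. A SAP that counted Non-CR/Non-PD would be departing from the written definition, so the defect is in stated text.

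The second reply is that little depends on it, and this largely stands. Phase 1 enrolment is complete and 68 mcg has been selected (Sections 3.1 and 3.2). The Phase 1 primary endpoint is DLT, and no decision rule uses DCR. The intervals above overlap almost entirely. The per-protocol set requires measurable disease (Section 9.2.3), so the sensitivity analysis leaves these patients out. PFS does not depend on the SD label.

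A reader might also infer more than the documents support:

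- **That Phase 2 DCR is affected in the same way.** Phase 2 requires measurable disease. An effect there would need central review to find no target lesion in an enrolled patient, and the documents give no rate for that.
- **That the minor-response rate has the same defect.** Section 9.6.1 states no denominator for it. Placing these patients in one rests only on the FAS default.
- **That differing ORR and DCR denominators are an error in themselves.** They are not. A patient without target lesions cannot have a PR but can have disease control.

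**Conclusion.** The point holds for Phase 1 DCR. Eligibility, the FAS default, the DCR definition and Tables 13-1 to 13-3 together leave a stable patient with only non-measurable disease in the denominator with no route to the numerator.

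The 33-point and 17-point effects in cohorts of 3 and 6 apply to each such patient, and only if that patient is progression-free at 24 weeks. The pooled range of about 1 to 11 points rests on the assumed n, m and p. The protocol does not say how many Phase 1 patients had only non-measurable disease, and if there were none the effect is zero.

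This is a modest defect in a descriptive secondary endpoint. It does not affect the Phase 2 primary ORR.

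**What to change.** Make two changes.

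1. In Section 9.6.1, extend the DCR definition: for patients without target lesions at baseline, Non-CR/Non-PD at least 24 weeks (± 1 week) after the start of study drug, with no earlier PD, counts as disease control.
2. In Table 13-3, add rows for patients with no target lesions at baseline. With no new lesions, non-target CR gives overall CR and non-target Non-CR/Non-PD gives overall Non-CR/Non-PD. Non-target PD, or any new lesion, gives PD, as the existing rows already provide.

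The cost is one sentence and a few table rows, with no new data. Although Phase 1 enrolment has closed, the change is still useful, because Section 9.1 carries later Phase 1 data into the final clinical study report.
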